### **2.5.2. Outliers**

All data will be included in the data analysis. No sensitivity analysis will be conducted with respect to any potential outliers.

## **2.6. Center Pooling Algorithm**

It is anticipated that some centers may randomize only a few patients. For the purpose of efficacy analyses, centers with less than 8 subjects in the FAS will be pooled with the closest center geographically until the number of subjects in the FAS after pooling is  $> 8$ . The pooled center will be used in models that adjust for center to minimize having a center where all subjects have the same treatment for the primary efficacy variable.

## **2.7. Data Handling Conventions and Transformations**

Selected by-subject listings will be presented for all subjects in the safety analysis set and sorted by subject ID number, treatment period, and study day (if applicable). Data collected on log forms, such as AEs and concomitant medications, will be presented in chronological order by preferred terms within subject.

## **2.8. Definitions of Baseline and Study Day**

### **2.8.1. Definition of Baseline**

There will be two definitions of baseline, for the Part 1 analysis and Part 2 analysis.

In the analysis of Part 1, baseline is defined as the last non-missing value before or at the run-in Visit 1 date.

In the analysis of Part 2, baseline is defined as the last non-missing value before or at the End of DB Period Visit 4 date.

### **2.8.2. Definition of Study Day**

Study day will be calculated differently in the analysis of Part 1 and Part 2.

For Part 1, study day for treated subjects will be calculated from the run-in visit date and derived as follows:

- For post Run-in Visit study days:  $\text{Assessment Date} - \text{Run-in Visit Date} + 1$
- For days prior to the Run-in Visit:  $\text{Assessment Date} - \text{Run-in Visit Date}$

Therefore, study day 1 in Part 1 is the day of the Run-in Visit.

For screen failures, study day will not be calculated.

For Part 2, study day for treated subjects will be calculated from the End of DB Period Visit 4 date and derived as follows:

- For post Visit 4 study days:  $\text{Assessment Date} - \text{Visit 4 Date} + 1$
- For days prior to Visit 4:  $\text{Assessment Date} - \text{Visit 4 Date}$

Therefore, study day 1 in Part 2 is the day of Visit 4.

## **2.9. Analysis Windows**

### **2.9.1. Analysis Visit Windows for OLE**

Subjects may not come to the visit in the OLE in accordance with the protocol schedule. For the purpose of analysis, visits will be assigned to the analysis visit windows as in [Table 3](#).

**Table 3: Analysis Visit Windows for OLE**

Visit	Nominal Time Point	Lower Limit (OLE Study Months)	Upper Limit (OLE Study Months)
Visit 4	--		0
Visit 5	Month 3	Month 3 - 1 month	Month 3 + 1 month
Visit 6	Month 6	Month 6 - 1 month	Month 6 + 1 month

OLE study month 0 is the start of the OLE visit day (Visit 4). Visits falling out of the above windows will not be assigned to a particular analysis visit. Data from these visits will be listed in listings.

- If multiple visits take place within a visit window, assignment of visits to visit window will be as follows:
  - The record closest to the nominal time point for that visit will be selected.
  - If there are 2 records that are equidistant from the nominal time point, the later one will be selected.

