## 1.2. Sample Size and Power

Part I of this study is a randomized, double-blind, placebo-controlled, 2-period, crossover outpatient study with a 6-week placebo run-in period.

Approximately 426 subjects will be enrolled to the placebo run-in period to randomize 288. With the 5:1 (high dose:low dose) randomization ratio for each of the two weight strata, it is estimated that 240 subjects will be randomized in the high-dose group and 48 subjects will be randomized to the lower dose level.

The sample size is based on detecting a difference in the percentage of subjects treated with a high dose (2.5 mg in the <50 kg weight stratum and 5 mg in the ≥50 kg weight stratum) who are pain free at 2 hours between ZNS and placebo. In this crossover trial, 240 high-dose-treated subjects will be adequate to detect a clinically relevant difference of 0.11 in the percentage of subjects who are pain free at 2 hours between ZNS and placebo as statistically significant (0.05, two tailed) with 90% power assuming a standard deviation of 0.5.

Approximately 48 subjects will be randomized in the low dose level (1 mg in the <50 kg weight stratum and 2.5 mg in the ≥50 kg weight stratum). The data from the low dose level will be summarized to explore dose-response relationship.

Based on other migraine crossover studies, dropout rates during the placebo run-in period ranged from 12% to 50%. Based on this, approximately 426 subjects will be enrolled into the placebo run-in period to randomize 288. This allows for approximately 32% dropout during placebo run-in period.

Approximately 100 subjects who complete the double-blind crossover phase will enter the 6-month OLE to enable at least 50 subjects to complete at least 6 months treating on average at least one migraine attack per month (treating up to 4 migraine attacks per month) with ZNS. Part II of the study is an OLE with subjects who successfully complete Part I of the study.

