## **6.2. Laboratory Evaluations**

Laboratory data are collected at Screening, Visit 4, and at End of Study for this study. Laboratory data collected will be summarized using the safety analysis set for Part 1 and using the OLE analysis set for Part 2. The analysis will be based on both values reported in SI units and in conventional units. Summaries in conventional units will be provided only for those parameters, for which conventional unit are different from the SI units.

A by-subject listings for laboratory test results will be provided by subject ID number and time point in chronological order for hematology, chemistry, urinalysis, and urine drug test, and pregnancy test. Values falling outside the normal reference range will be flagged in the data listings, as appropriate.

No formal statistical testing is planned.

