### **6.2.1. Summaries of Numeric Laboratory Results**

For Part 1, numeric laboratory results at Part 1 baseline and Visit4/End of Double-Blind Period as well as the change from baseline to end of double-blind period will be summarized using descriptive statistics (N, mean, standard deviation, median, minimum, and maximum) by treatment group.

For Part 2 numeric laboratory results will be similarly summarized for Part 2 baseline and Month 6 visit.

The proportion of subjects with Low (below the lower limit of normal range), Normal (within the limit of normal range), High (above the upper limit of normal range) will be presented for both parts.

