## 6.5. Electrocardiogram Results

Descriptive statistics of ventricular rate, PR interval, QRS interval, QT interval, corrected QT intervals (QTcF and QTcB), and RR interval will be provided at Part 1 baseline and End of Double-Blind period for Part 1 for the safety analysis set and also for Part 2 baseline and End of Study (Month 6) for the OLE analysis set. Change from the corresponding part baseline for these parameters will also be summarized.

The QT interval (measured in millisecond [msec]) is a measure of the time between the start of the Q wave and the end of the T wave in the heart's electrical cycle. The QT interval represents electrical depolarization and repolarization of the ventricles. The QT interval is affected by heart rate, and a number of methods have been proposed to correct QT for heart rate.

Corrected QT (QTc) intervals will be derived using Fridericia's correction (QTcF) as follows:

$$QT_{cF} = \frac{QT}{\sqrt[3]{RR}}$$

where QT is measured in msec;  $RR = 60/\text{Heart Rate}$  (beats per min [bpm]) and RR is measured in seconds

Corrected QT (QTc) intervals will be derived using Bazett's correction (QTcB) as follows:

$$QT_{cB} = \frac{QT}{\sqrt{RR}}$$

where QT is measured in msec;  $RR = 60/\text{Heart Rate}$  (beats per min [bpm]) and RR is measured in seconds

ECG overall interpretation and rhythm assessment will also be summarized categorically by visit for both parts.

ECG results will also be summarized based on the following categories.

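### Table 3's visit windows, combined with Month-6-only displays, leave final open-label assessments made before month 5 or after month 7 out of four Part 2 safety summaries

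*SAP*

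**What the plan says.** **Windows.** Section 2.9.1 expects open-label visits to stray from schedule and assigns them through Table 3. The lower limit for Visit 5 is "Month 3 - 1 month" and for Visit 6 "Month 6 - 1 month"; the upper limits are one month after the nominal time. For anything else: "Visits falling out of the above windows will not be assigned to a particular analysis visit", and "Data from these visits will be listed in listings". Table 3 has no early-termination or last-value category.

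**Collection.** Section 6.2: "Laboratory data are collected at Screening, Visit 4, and at End of Study for this study". Visit 4 is the Part 2 baseline, so End of Study is the only post-baseline laboratory time point named for Part 2.

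**Display.**
- Numeric laboratory results and change (6.2.1): "For Part 2 numeric laboratory results will be similarly summarized for Part 2 baseline and Month 6 visit".
- Laboratory shifts (6.2.2): from Part 2 baseline to End of Study (Month 6).
- ECG intervals and their change (6.5): "Part 2 baseline and End of Study (Month 6) for the OLE analysis set".
- Physical findings (6.7): Part 2 baseline and End of Study (Month 6).

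**Completion.** Section 6.8 counts a child as completing six months if the extension was completed and Visit 6 came at least 180 days after Visit 4. It sets no upper limit.

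**The concern.** Part 2 is a safety extension. A child who leaves early can have only one post-baseline laboratory set in Part 2, the one taken at the end of participation. Table 3 places that set either in no window or in the Month 3 window, and the four summaries above show neither. A late Visit 6 has the same fate: the child can be a six-month completer under Section 6.8 and still be absent from the Month 6 tables.

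These four summaries would therefore describe mainly children followed for five to seven months. If leaving is related to tolerability, the missing values are a selected group. Two programmers could also build different tables, because the SAP does not say whether End of Study (Month 6) means the windowed visit or the final visit whenever it occurs.

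**Working it through.** The SAP states no figure for this loss, so there is nothing to reproduce. The check follows a final assessment through the rules and then sizes the loss under stated assumptions.

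**Step 1. Where a final assessment goes (Table 3 with Sections 6.2.1, 6.2.2, 6.5 and 6.7)**

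| Time of final assessment | Table 3 assignment | In the four Month 6 summaries? |
|---|---|---|
| Before month 2 | none, listed only | no |
| Months 2 to 4 | Visit 5 (Month 3) | no |
| Between months 4 and 5 | none, listed only | no |
| Months 5 to 7 | Visit 6 (Month 6) | yes |
| After month 7 | none, listed only | no |

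Table 3 does not convert months to days. With the 30-day months that Section 6.8 uses for its own summary, month 7 ends at 7 × 30 = 210 days. A Visit 6 on day 220 would then satisfy the 180-day completion rule but fall outside the window.

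**Step 2. Size**

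Inputs: N = 100 entrants (Section 1.2). The early-stop fraction s is not given, so it is assumed to lie between 10% and 50%. Further assumptions: stop times uniform over months 0 to 6, one assessment at stopping, and every completer seen within months 5 to 7.

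Of the early stops:
- unassigned: (2 + 1)/6 = 3/6
- placed at Visit 5: 2/6
- reaching Month 6: 1/6

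So 5/6 are missing from the four summaries.

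- Missing = N × s × 5/6
- Month 6 n = N(1 − s) + N × s/6
- Completer share = N(1 − s) / Month 6 n

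| s | Completers | Early stops in Month 6 window | Month 6 n | Missing | Completer share |
|---|---|---|---|---|---|
| 10% | 90 | 1.7 | 91.7 | 8.3 | 98% |
| 30% | 70 | 5.0 | 75.0 | 25.0 | 93% |
| 50% | 50 | 8.3 | 58.3 | 41.7 | 86% |

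**Step 3. Sensitivity to the shape of stopping**

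With a constant hazard and 50% stopped by month 6, λ = ln 2 / 6. The proportion stopped before month 5 is 1 − exp(−5λ) = 0.439, or about 44 of 100. The uniform assumption gives 42, so the shape matters little here. Visits after month 7 would add to these counts.

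**Step 4. What the windows do not touch**

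- Treatment-emergent adverse events are assigned by dose and onset date and summarized for the OLE analysis set (6.1.6, 6.1.7).
- C-SSRS has an overall summary of any post-baseline occurrence as well as by visit (6.6).
- Vital signs are summarized at every visit (6.3), and ECG interpretation and rhythm by visit (6.5). A Visit 5 assignment can enter both; only unassigned visits are lost.
- The low/normal/high laboratory proportions (6.2.1) and the Table 6 ECG categories name no visit, so their treatment is open.

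**The case against.** **The label may already cover early final visits.** End of Study (Month 6) could be meant as the last visit whenever it happens, and the protocol, which is not at hand, may specify early-termination procedures. The SAP mentions no early-termination assessment, so it is not established that every early leaver has laboratory tests or an ECG at stopping. This stands as a limit on the size. It does not remove the point: under that reading the label contradicts the Table 3 rule, and Section 6.2.1 refers to the Month 6 visit outright.

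**A reader might infer that the Part 2 safety tables as a whole leave out early leavers.** The SAP does not support that. Step 4 of the working shows that the adverse event tables and the overall C-SSRS summary do not depend on the windows, and that several by-visit tables are only partly affected. Section 3.1 also reports discontinuations with reasons for all who entered Part 2, and the excluded data are listed, with out-of-range laboratory values flagged.

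**A reader might infer that about half the children would be missing,** because Section 1.2 says "Approximately 100 subjects who complete the double-blind crossover phase will enter the 6-month OLE to enable at least 50 subjects to complete". That sentence goes on to require an average of at least one treated attack per month. A child who completes with fewer attacks is outside the 50 but still has a Month 6 assessment. At least 50 is also a floor on a target, not a forecast of early stopping.

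**A reader might infer a bias towards a benign picture.** That is plausible if children stop for tolerability. The SAP gives no distribution of reasons, and stopping could equally reflect few attacks, lack of effect or logistics.

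**Conclusion.** The point holds for four Part 2 summaries: numeric laboratory values with change, laboratory shifts, ECG intervals and physical findings. Applied as written, Table 3 together with the Month-6-only displays leaves out any final assessment before month 5 or after month 7. The alternative reading of End of Study (Month 6) avoids the loss only by conflicting with Table 3.

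Under uniform stopping with one assessment at stopping, the loss is about 8 of 100 entrants at 10% early stops, 25 at 30% and 42 at 50%. These rates are assumptions, not SAP figures. Neither the size nor the direction of any bias is shown by the document. The correction is worth making before the final analysis because it is cheap and concerns tables whose purpose is safety.

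**What to change.** - Add to Table 3 a derived Part 2 analysis visit, End of Study: the last post-baseline open-label assessment, including early termination, regardless of window.
- Use it for the numeric laboratory, laboratory change, laboratory shift, ECG interval and physical-exam tables, and replace the label End of Study (Month 6) in Sections 6.2.2, 6.5 and 6.7 to match.
- State that the low/normal/high laboratory proportions and the Table 6 ECG categories use any post-baseline open-label value.
- Keep the Month 3 and Month 6 windows for by-visit displays.

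The cost is SAP wording and one extra derivation. It uses assessments already collected, so far as the trial takes them at early stopping. The drawback is that an End of Study column mixes different lengths of exposure, so it should stand beside the windowed Month 6 column, each with its own n.

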### 2.9.2. Analysis Windows for Diary Data

Diary assessment may not occur exactly at the protocol-specified time points. For the purpose of analysis or Part 1, observations will be assigned to analysis windows.

The analysis windows for diary data in Part 1 are provided in [Table 4](#).

**Table 4: Analysis Windows for Diary Data**

Nominal Time Point	Lower Limit from Dosing Time (Minutes)	Upper Limit from Dosing Time (Minutes)
headache first became severe or moderate	-60	0
30-minute	1	45
1-hour (60 minutes)	46	90
2-hour (120 minutes)	91	150
24-hour (1440 minutes)	151	2160

Diary records falling out of the windows above will not be assigned and will only be listed in listings.

If multiple, valid, nonmissing diary data exist in an analysis window, records will be chosen based on the following rules:

- In general, the predose value will be the last nonmissing value prior to the dosing time of study drug.
- For postdose assessments:

- The record closest to the nominal time for that visit will be selected.
- If there are 2 records that are equidistant from the nominal time, the nominal record (the one recorded on the correct diary time point) will be selected.
  - However, if there are 2 records that are equidistant, one is the actual time and one is the imputed time (due to missing data), the assessment with actual time will be selected.
- If there are 2 records with identical times, the one recorded on the correct diary time point will be used.

In the analysis of Part 2 the diary observations will be analyzed according to the nominal timepoint recorded in the diary.

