Eligible placebo non-responders will be randomized to one of two treatment sequences within their respective body weight stratum determined immediately prior to randomization: ZNS followed by placebo or placebo followed by ZNS ([Table 1](#)). Subjects weighing less than 50 kg will be allocated randomly to receive ZNS 2.5 mg or 1 mg in a 5:1 fashion during the ZNS treatment. Subjects weighing at least 50 kg will be allocated randomly to receive ZNS 5 mg or 2.5 mg in a 5:1 fashion during the ZNS treatment ([Table 2](#)). Following randomization, subjects will have up to 6 weeks to treat a migraine attack of moderate or severe intensity. During each treatment period, subjects will treat a single moderate to severe migraine attack with study drug within approximately 20 minutes of the headache pain reaching moderate or severe intensity. Headaches occurring while the child is at school will not be treated with study drug. Headache pain intensity will be assessed by the subjects immediately prior to treatment with study drug and at 30 minutes, 1, 2, and 24 hours postdose using a subject diary containing the 4-point headache pain intensity scale. Associated migraine symptoms will also be assessed at these time points. Subjects who do not obtain satisfactory relief of migraine pain by 2 hours after taking study drug will be permitted to treat with their protocol-allowed pre-study acute migraine medication (eg,

nonsteroidal anti-inflammatory drugs [NSAIDs] or acetaminophen) at that time or at any time thereafter, if the headache does not resolve or if it recurs, with the exception that all triptans and ergot derivatives are prohibited for 24 hours following the dose of study treatment. After treating a migraine attack in the first treatment period, the subject will return to the study site to receive study drug for the second treatment period. Subjects will then have up to 6 weeks to treat a second migraine attack of moderate or severe intensity.

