### **2.5.1.1. Imputation Method for Migraine Headache Diary Data**

1. If the predose diary is missing the pain intensity for a particular treatment period, then the subject is considered a non-responder for diary time points 0.5-hour, 1-hour, and 2-hour for that treatment period.
2. If all postdose pain intensity up to and including the 2-hour diary are missing for a particular treatment period, then the subject is considered a non-responder for those time points (0.5-hour, 1-hour, and 2-hour) for that treatment period.
3. If a subject receives rescue medication within 2 hours after dosing with study drug for a particular treatment period, the subject will be considered a non-responder for all the subsequent diary time points after rescue for that treatment period up to and including the 2-hour time point. Note: if subject diary includes records of rescue medication that started prior to the start of migraine, such medications will be ignored as incorrect diary entry. If rescue medications are recorded with missing start date/time, worse case will be assumed, i.e. that the rescue medication was taken at the same time as the migraine started.
4. If a subject naps or sleeps within 2 hours after dosing with study drug for a particular treatment period, the subject will be considered a non-responder for all diary time points up to and including the 2-hour diary time point for that treatment period.
5. No imputation will be done for the 24-hour time point (observed cases only).
6. Otherwise, missing diary data up to the 2-hour time point will be imputed by the last observation carried forward (LOCF).

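### The Part 1 24-hour diary window opens at 151 minutes, so a late 2-hour page is analysed as the observed 24-hour value when no true 24-hour entry lies in the window

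*SAP*

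**What the plan says.** In the double-blind periods, pain is rated predose and then "at 30 minutes, 1, 2, and 24 hours postdose using a subject diary containing the 4-point headache pain intensity scale" (SAP section 1.1). Nothing is scheduled between 2 and 24 hours.

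Section 2.9.2 assigns Part 1 diary records by time since dosing: "For the purpose of analysis or Part 1, observations will be assigned to analysis windows". Two rows of Table 4 matter here: "2-hour (120 minutes) 91 150" and "24-hour (1440 minutes) 151 2160". When a window holds more than one valid postdose record, "The record closest to the nominal time for that visit will be selected". The page on which a rating was entered counts only when two records are equally distant from nominal or have identical times. Part 2 is handled differently: "In the analysis of Part 2 the diary observations will be analyzed according to the nominal timepoint recorded in the diary".

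On missing data, section 2.5.1.1 says in rule 5: "No imputation will be done for the 24-hour time point (observed cases only"). Rule 6 covers the earlier time points: "Otherwise, missing diary data up to the 2-hour time point will be imputed by the last observation carried forward (LOCF").

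**The concern.** A 24-hour outcome should describe the patient about a day after dosing. With a lower limit of 151 minutes, a 2-hour page filled in slightly late leaves the 2-hour window and drops straight into the 24-hour window. If nothing closer to 1440 minutes is there, that rating is reported as an observed 24-hour result.

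Rule 5 of section 2.5.1.1 evidently means a missing 24-hour rating to stay missing. Table 4 can instead fill the gap with a rating taken about 21 hours too early.

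The results exposed in section 5.3 are pain-free status, headache response, and absence of photophobia, phonophobia and nausea, each at 24 hours. The 24-hour level of the repeated-measures model in section 5.2.1.6 is exposed too. The section 5.3 proportions are analysed by GEE, so the misassigned ratings would enter inferential results and not only listings.

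**Working it through.** **Inputs.** Window limits and nominal times are from Table 4, the selection rule from section 2.9.2, and the missing-data rules from section 2.5.1.1. The limits are stipulated without a derivation, so there is no plan figure to reproduce.

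**Step 1: tolerance around each nominal time.** Early tolerance = nominal − lower limit. Late tolerance = upper limit − nominal. Width = upper − lower + 1, counting both end minutes.

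| Time point | Window (min) | Early | Late | Width |
|---|---|---|---|---|
| 30 min | 1 to 45 | 30 − 1 = 29 | 45 − 30 = 15 | 45 |
| 1 h | 46 to 90 | 60 − 46 = 14 | 90 − 60 = 30 | 45 |
| 2 h | 91 to 150 | 120 − 91 = 29 | 150 − 120 = 30 | 60 |
| 24 h | 151 to 2160 | 1440 − 151 = 1289 | 2160 − 1440 = 720 | 2010 |

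The 24-hour row accepts a record 1289/60 ≈ 21.5 hours early. The postdose windows run without a gap from minute 1 to minute 2160, so the rule that out-of-window records are only listed catches nothing postdose before 36 hours.

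**Step 2: apply the rules to test diaries.** Entries are (minute, pain score).

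- (30, 2), (60, 0), (155, 0), no 24-hour entry. The 155-minute record is alone in the 24-hour window and becomes the 24-hour value, pain free. The 2-hour window is empty, so rule 6 carries the 60-minute score forward, provided no rescue or sleep rule applies.
- (30, 2), (95, 0), (155, 0), no 24-hour entry. The 95-minute record is the 2-hour value and the 155-minute record is the 24-hour value.
- (30, 2), (60, 2), (155, 0), no 24-hour entry. The 24-hour value is pain free. The 2-hour value is carried forward as moderate pain, so there is no 2-hour response.
- First diary plus (1440, 2). Distances are 0 and 1440 − 155 = 1285, so the true entry is used.
- First diary plus (2160, 2). Distances are 720 and 1285, so the true entry is used.
- First diary plus (2161, 2). That entry is outside the window, so the 155-minute record is used.

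**Step 3: when the fault occurs.** Any entry from 720 to 2160 minutes is at most 720 minutes from nominal. Any entry from 151 to 719 minutes is at least 1440 − 719 = 721 minutes away. A genuine entry from 720 minutes onward therefore always displaces a late 2-hour page completed before 720 minutes. The fault needs the 24-hour entry to be absent or later than 2160 minutes.

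**Step 4: effect of a 720-minute lower limit.** Minutes 151 to 719 would leave the window: 719 − 151 + 1 = 569 of 2010, or 28%. The 155-minute record would then be listed only and the 24-hour value would be missing, as rule 5 intends.

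**The case against.** The best defence is that the closest-to-nominal rule already protects every subject who completes the 24-hour page on time. That is correct, and it confines the problem to missing or very late 24-hour entries. It does not help those subjects, because the rule has nothing to choose between when the late page is the only record in the window.

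Several stronger readings are tempting, but the document does not support them:

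- **That the primary result is at risk.** The primary endpoint in section 5.1 is pain-free status at 2 hours, and the 24-hour window does not enter it.
- **That a late 2-hour page by itself creates a sustained response.** Section 5.3 also requires a 2-hour response. A record after 150 minutes cannot supply one, so it must come from LOCF or from another record at 91 to 150 minutes. The third test diary shows a 24-hour responder who is not sustained.
- **That recurrence and sustained response are certainly affected.** Section 5.3 does not say which records define them. Use of the windowed 24-hour value is a natural inference from the schedule, but only an inference.
- **That Table 4 contradicts rule 5.** A 155-minute rating is an observed value placed by a stated window, so the wording of the rule is not breached. Its purpose is.
- **That a percentage of affected attacks, or a bias in favour of one treatment, can be stated.** The SAP gives no rate of late 2-hour or missing 24-hour entries and nothing on how either differs by treatment.
- **That the whole window should be narrowed.** The fault lies at the lower limit. Nothing shown here counts against the 36-hour upper limit, and cutting it would discard true 24-hour pages.

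**Conclusion.** The point holds in this limited form. As written, Table 4 makes a 2-hour page completed after 150 minutes the observed 24-hour value whenever no record closer to 1440 minutes lies in the window. In effect a rating of about 2.5 hours is carried forward to 24 hours.

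The consequence is confined to the secondary 24-hour endpoints and the 24-hour level of a supportive GEE. Recurrence and sustained response join them if they are built on the windowed value. Neither size nor direction can be computed: the share of attacks affected is the proportion with no usable 24-hour entry multiplied by the proportion of those with a postdose entry after 150 minutes, and the document gives neither.

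This should be fixed, because the rule gives a wrong 24-hour result in identifiable cases and is easy to repair. It does not threaten the trial's main conclusion.

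**What to change.** Make one or both of these changes to section 2.9.2 and Table 4 before unblinding Part 1:

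1. State that a record entered on the 0.5-, 1- or 2-hour diary page may not be assigned to the 24-hour time point.
2. Raise the lower limit of the 24-hour row, for example to 720 minutes, which matches the existing late tolerance of 720 minutes (1440 − 720 = 720). Leave the upper limit at 2160 minutes. Records between the two windows are listed only.

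Either change removes the 155-minute case. The first alone would still admit a 24-hour page completed far too early. The second alone would still admit a 2-hour page completed at 720 minutes or later. Using both closes both routes.

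It would also help to say in section 5.3 whether recurrence and sustained response are derived from the windowed 24-hour value.

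The cost is one table row and a sentence or two. Some 24-hour values that would have been filled by early ratings will be missing, which is what the observed-cases rule calls for.
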